We have extensive experience using hdEEG technology to study brain activity and sleep abnormalities in various neuropsychiatric conditions, including insomnia. We have identified sleep spindle abnormalities in schizophrenia, which have been suggested to have an etiopathologic role in the disorder and may be one of the most specific biomarkers for the disorder (Ferrarelli et al 2007, Ferrarelli et al 2010). In depression, we have found evidence for abnormalities in sleep homeostasis through analyses of brain activity during sleep and wakefulness prior to and following nocturnal sleep (Goldstein et al 2012, Plante et al 2013b) as well as a regionally specific decrease in slow waves in hypersomnolent depressives (Plante et al 2012b). Our preliminary work in insomnia under previously approved protocols H-2007-0150, and continuing with H-2009-0019, (comparing 9 subjects with primary insomnia, 9 age- and sex-matched depressives and 9 matched healthy sleepers, Table 1) revealed that beta and gamma activity were increased globally in both insomnia and depression in comparison to controls, but only alpha activity, particularly in deeper sleep (stage N3) distinguished primary insomnia from depressed and control subjects. Notably, when localized in the cortex, these increases in alpha during N3 sleep were most prominent in primary sensory and associative cortices (including somatosensory, auditory and visual cortices), suggesting that even during the deepest stage of sleep, sensory areas are still relatively active in insomnia relative to controls (Figure 2). Our primary aim, then, would be to extend and confirm this result in a larger group of primary insomnia participants in

	PI (N= 9)		MDD (N= 9)		GSC (N= 9)		Overall ANOVA			t tests (uncorrected)		
	Sex (m/f)		Sex (m/f)		Sex (m/f)		df	F	p	1 vs. 2	1 vs. 3	2 vs. 3
Age (years)	3/6		3/6		3/6		—	—	—	—	—	—
HRSD-17	5.56 (2.07)		16.00 (4.54)		—		—	—	—	—	—	—
ISI	17.67 (3.81)		—		—		—	—	—	—	—	—
ESS	6.11 (4.01)		—		—		—	—	—	—	—	—
TST (min)	361.89 (45.06)		384.33 (48.52)		386.22 (38.07)		2,24	0.85	.441	—	—	—
WASO (min)	86.89 (29.68)		45.17 (24.33)		23.39 (23.30)		2,24	13.94	< .001	.007	< .001	.262
AI (#/hr.)	11.96 (5.47)		11.11 (7.66)		9.43 (9.86)		2,24	0.24	.789	—	—	—
SE (%)	79.07 (6.40)		86.06 (5.82)		92.61 (5.53)		2,24	11.76	< .001	.059	< .001	.083
SOL (min)	8.67 (8.76)		17.28 (17.89)		7.94 (8.99)		2,24	1.52	.238	—	—	—
N1 (%)	12.54 (5.39)		9.36 (7.13)		7.24 (3.48)		2,24	2.09	.146	—	—	—

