2.3 Defining abnormal activity during sleep transitions in insomnia with hdEEG

[figure not shown]

Figure 3: The relative involvement of sensory brain regions in slow waves progressively increase during the descent into sleep.
 Cortical flat map shows significantly different slow wave involvement (based on the Wilcoxon Signed rank test, 6 subjects) when comparing the early (2-3, red) to late (8-9, blue) falling asleep periods. To compare results obtained in different epochs and subjects, relative involvement is computed as the ratio between the value in each voxel and the value resulting from the average of all brain voxels. Modified from Siclari et al. *in preparation*.

subjects to systematically wake them up throughout the night) in a group of normal subjects to describe how different waveforms contribute to falling asleep in a regionally specific manner by examining hdEEG during equally distributed time periods between the end of posterior alpha (10-20 channel Oz) and the first slow wave burst (2 consecutive slow waves without an arousal (Siclari et al. *in preparation*). In good sleeping controls, slow waves followed two spatially and temporally distinct processes during the transition from wakefulness to sleep. The early process was characterized by isolated, large amplitude slow waves that involved mainly the frontal regions and was associated with high gamma power. The late process was marked by numerous smaller slow waves that tended to originate more diffusely over the cortex, and to involve also the temporal, lateral parietal and occipital brain regions. The falling asleep process is thus characterized by a transition from predominantly local to increasingly global sleep patterns. This process may be disrupted in insomnia, particularly given the similarities between areas from which slow waves involved only later in the falling asleep process originate and areas exhibiting alpha activity during deep NREM sleep in insomnia patients.

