2. Define cortical source abnormalities in the processes of falling asleep and arousing from sleep in insomnia patients with and without depression compared to healthy sleeping controls.

3.2 Secondary Objectives:

1. Correlate abnormalities in sleep EEG patterns with specific insomnia symptoms, including sleep onset difficulties, sleep maintenance problems, nonrestorative sleep and daytime dysfunction.

Insomnia and Sleep Patterns Study

2. Define abnormalities in overnight changes in waking EEG activity in insomnia patients with and without depression compared to healthy sleeping controls.
3. Explore whether abnormalities in sleep and waking EEG activity in insomnia patients, with and without depression, normalize following treatment with a sleep medication.

3.3 Clinical Hypotheses:

1. Insomnia patients will show increased regional EEG alpha activity in sensory cortical areas particularly during sleep.
2. Insomnia patients will show abnormalities in the process of sleep initiation, including regional sources of high frequency EEG activity that will interfere with the normal progression of the sleep process.
3. Insomnia patients will show abnormalities in the regional patterns of cortical arousal responses to external stimuli during sleep, particularly in the sensory cortical areas exhibiting increased alpha activity.
4. Abnormalities in sleep EEG patterns may be correlated with specific insomnia symptoms, particularly difficulty with sleep initiation or maintenance.
5. Waking EEG in insomnia patients will not show overnight recovery compared to controls, which will be correlated with specific EEG abnormalities during sleep, such as elevations in higher frequency activity.
6. Explore whether insomnia patients with and without depression differ in abnormalities in sleep EEG patterns.

4. Research Design and Methods

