order of minutes instead of hours. Preliminary results suggest that tonic alpha power during N3 sleep may distinguish between these groups, but it is also conceivable that events like slow waves or spindles may provide additional distinguishing information, and windows around these events may be relevant. The **outcome measure** addressing **this first primary study objective** will be the cortical localization maps of band-pass filtered EEG data in the frequency range of interest (identified by the scalp-level analysis from the initial steps, e.g. alpha) using a distributed inverse solution (i.e. LORETA, for details of the methods involved see (Murphy et al 2011)). All group comparisons of distributed source localization maps will be analyzed using statistical nonparametric mapping (SnPM)(Nichols & Holmes 2002) which is ideally suited to address the multiple comparison issues inherent to neuroimaging and which does not make unwarranted assumptions about data distribution. This method has been successfully applied in a number of hdEEG studies in our laboratory (Ferrarelli et al 2007, Huber et al 2006, Huber et al 2004), and compares favorably with Statistical Parametric Mapping for analyses having low degrees of freedom.

Falling asleep imaging (Primary Objective 2a)

During both the baseline and serial awakening sleep nights, the descent into (or back into) sleep will be analyzed by dividing the interval between the last appearance of occipital alpha and the first instance of a burst of slow waves (more than 2 slow waves consecutively without an arousal) into 10 equally spaced temporal bins prior to cortical source estimation. Distributed source localization maps for individual frequency ranges will then be average within subject and then within group prior to statistical analysis.

Sleep arousal imaging (Primary Objective 2b)

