During both the baseline and serial awakening sleep nights, spontaneous arousals/awakenings will also be explored using similar methods to the falling asleep analysis except the windows of interest will be fixed at 12 seconds (10 intervals = 2 minutes) given that there is no *a priori* criteria for establishing the arousal onset. Additionally, for the serial awakening sleep nights, stimulus evoked responses during sleep will be examined using similar methods as described above, both in time (evoked potential analysis) and time-frequency (event related spectral perturbation) as we have done previously (Landsness et al 2009, Riedner et al 2011) except the analysis window will be temporally fixed around the stimulus trigger (15 sec window, including 2 seconds before and 3 seconds after 10 second auditory stimulus onset and offset, respectively). Arousals will be scored according to established arousal criteria (Bonnet et al 2007). Stimuli will be categorized into those that did not cause an arousal, those that did cause an arousal, and those that resulted in a full awakening. The **outcome measures** addressing the second primary objective will be similar to the outcome measure for the first primary objective, cortical localization maps of band-pass filtered EEG data, except that the temporal windows of interest will be predefined as described above. Further exploratory analyses will employ Cox regression (see McKinney et al) to investigate the ability of alpha in particular cortical regions of interest (defined in the baseline analysis) to predict sleep stability in insomnia patients and controls.

Correlations between EEG abnormalities and behavioral variables

Comparison of behavioral data, as well as traditional sleep architecture variables will be analyzed using established procedures (e.g. ANOVA for repeated measures and post-hoc tests).

Insomnia and Sleep Patterns Study

Correlations with EEG and/or source localization of power will either be examined using a region of interest approach or using SnPM techniques to explore cortical areas whose activity may be related to the variable of interest, depending on the nature of the exploratory analysis.

Waking EEG and Evoked Potentials analysis

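### Falling asleep and spontaneous arousals (Primary Objective 2): with no between-bin contrast named, a constant group difference in EEG power could not be told apart from an altered process

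*Combined protocol and SAP*

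**What the plan says.** **The question.** Section 3.1 sets Primary Objective 2 as: "Define cortical source abnormalities in the processes of falling asleep and arousing from sleep in insomnia patients with and without depression", compared with healthy sleepers. Hypothesis 2 in section 3.3 expects abnormal sleep initiation, including "regional sources of high frequency EEG activity that will interfere with the normal progression of the sleep process".

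**The analysis (section 4.4.2).**
- Falling asleep (2a): the interval from the last occipital alpha to the first slow-wave burst is divided "into 10 equally spaced temporal bins prior to cortical source estimation". Maps per frequency range are then averaged within subject and within group before testing. The text does not say whether that averaging runs over descents only or over bins as well.
- Spontaneous arousals (2b): similar methods, with ten fixed windows of 12 seconds. The plan states that it has no prior criterion for when an arousal begins.
- Outcome for Objective 2: similar to that of Objective 1, namely "cortical localization maps of band-pass filtered EEG data, except that the temporal windows of interest will be predefined as described above".
- Test: SnPM for every group comparison of source maps.
- Tones (2b): evoked potentials and event-related spectral perturbation, in a window that includes 2 seconds before the stimulus.

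**Expected constant differences.** Section 2.2 reports from the pilot that "beta and gamma activity were increased globally in both insomnia and depression in comparison to controls". Hypothesis 1 predicts raised regional alpha, particularly during sleep. Section 4.4.2 cites tonic alpha in N3 as a likely discriminator.

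**The concern.** A process is a course over time. The null hypothesis that matches it is the same course across the ten bins in patients and controls. The declared outcome is a level: source power in a window. Permuting group labels on level maps generates the null of equal level. The two nulls part company as soon as one group is higher by a constant amount throughout, and the documents lead one to expect exactly that.

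SnPM does not help here. It handles multiplicity over sources and takes the tested quantity as given.

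Elsewhere the authors do name or use within-person contrasts. The waking-EEG analysis in section 4.4.2 plans evening against morning. The group's own falling-asleep work in section 2.3 (Figure 3) looked at slow-wave involvement "when comparing the early (2-3, red) to late (8-9, blue) falling asleep periods", on values scaled to the whole-brain mean. Neither device is carried into section 4.4.2 for 2a or spontaneous arousals.

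At stake is whether the second primary objective adds anything to the first. A positive level map in these windows might only re-measure the tonic difference already examined under Objective 1.

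**Working it through.** **Inputs from the documents.** 20 per group, two-sided alpha 0.05, pilot d = 1.15 (section 4.4.1); ten bins (section 4.4.2).

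**Assumptions.** Offsets d = 0.5 and 0.8 as well as 1.15; correlation between bins within a person of 0.3, 0.6 and 0.9; equal variances; one region; an additive offset.

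**1. The plan's own figure.** Two-sample t-test, df = 38, noncentrality d × √(n/2) = 1.15 × √10 = 3.64. Power is 94.3%, against about 94% stated. With 10 per group it is 68.2%, against 68% stated. Both are reproduced.

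**2. One bin, constant offset, same course.** The level test in a single bin is this same t-test, so it rejects in 34%, 69% and 94% of trials at d = 0.5, 0.8 and 1.15.

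**3. Ten bins with Bonferroni, or pooled.** Both groups get the same linear course and one gets a constant offset; 4,000 runs per setting. Each bin is tested at 0.05/10 = 0.005. Cells show rejection (%) at bin correlation 0.3 / 0.6 / 0.9.

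| Offset d | At least one bin, Bonferroni | Mean of ten bins | Group-by-bin | Slope over bins |
|---|---|---|---|---|
| 0 | 4.5 / 3.2 / 2.0 | 4.7 / 4.5 / 5.0 | 5.3 / 4.5 / 5.1 | 5.2 / 4.8 / 5.1 |
| 0.5 | 50.4 / 36.3 / 19.5 | 71.9 / 48.6 / 35.4 | 5.6 / 5.7 / 4.6 | 4.7 / 4.7 / 4.4 |
| 0.8 | 89.8 / 75.8 / 54.2 | 98.1 / 86.8 / 74.1 | 5.2 / 5.4 / 5.3 | 5.4 / 5.5 / 5.0 |
| 1.15 | 99.8 / 97.5 / 88.7 | 100 / 99.3 / 96.2 | 5.0 / 5.4 / 5.3 | 4.9 / 5.3 / 5.2 |

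One repeat gave 21–47%, 54–89% and 87–100% for the Bonferroni column. Another, with 20,000 runs, gave 21–49%, 55–90% and 88–100%, with bins 8–9 minus 2–3 rejecting in 4.7–5.2%. The ranges quoted elsewhere in this point span these runs.

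The pooled column can be checked by hand. The mean of ten bins has SD √(ρ + (1 − ρ)/10). At ρ = 0.9 this is √0.91 = 0.954, so d = 1.15 becomes 1.15/0.954 = 1.21 and power is 96.0%.

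**4. Whole maps.** With 200 correlated sources, max-|t| over 300 label permutations, correlation 0.7 and 150 trials per setting, a given bin map is significant in 25%, 64% and 95% of trials. The late-minus-early map is significant in 3–7%. Counting any bin without correction already gives 33% at d = 0. That is multiplicity, a separate matter, so the Bonferroni figures are the ones to use.

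**5. Noise of the contrast.** With single-bin variance 1, a difference of two single bins has variance 2(1 − ρ), which exceeds 1 when ρ < 0.5. A difference of two-bin means has variance 1 − ρ.

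**The case against.** **The plan leaves the test open.** A reader might infer that groups are compared bin by bin. The text does not say so. It does not state how bins enter the test, and it refers to an outside paper for details of source localisation. This stands: the defect is a contrast that is not named, and no wrong contrast has been chosen. It does not remove the problem, because testing bins singly and pooling them both fail, and only a contrast that the plan does not name would avoid it.

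**A level difference is partly of interest.** A reader might call every level finding a false positive. Hypothesis 2 does not support that: it counts regional high-frequency sources during sleep initiation as an abnormality. This stands, so level maps should remain a result. What they cannot show alone is the second half of that hypothesis, interference with normal progression.

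**The pilot effect was measured elsewhere.** d = 1.15 is averaged over a cluster already found significant. Figure 2 takes its data from the middle of the first NREM episode, whereas the 2a window precedes established sleep. Section 2.2 leaves open whether the alpha increase is specific to N3, and it gives no effect size for beta and gamma. This stands: the 1.15 row is illustrative and not a forecast.

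**Much of the work is declared exploratory.** Section 4.4.2 says so of the protocol at large, and there is no formal rule for declaring Objective 2 positive. This lowers the urgency. Objective 2 is nevertheless listed as primary, with a named outcome measure.

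**Normalisation might help.** The whole-brain ratio used for Figure 3 would remove a uniform proportional offset, but not a regional alpha offset, and it is not in section 4.4.2.

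**Conclusion.** The point holds for falling asleep and for spontaneous arousals. As written, the analysis could not separate a tonic group difference from an altered process. At a moderate offset of d = 0.5, a difference with no change in course would still give at least one significant bin after Bonferroni in roughly 20–50% of trials. The figure is 54–90% at d = 0.8 and 87–100% at d = 1.15. Tests of change over bins hold about 5%.

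These sizes rest on an assumed constant offset and assumed bin correlations. The documents give neither for these windows.

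Two wider readings are not supported. The point does not cover all of Objective 2, since event-related spectral perturbation measures change around the stimulus; only its baseline correction is left unstated. Nor does the plan imply that near-certain false claims will follow, since the offset at sleep onset or before arousals is unknown.

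**What to change.** Add to section 4.4.2, for 2a and spontaneous arousals:

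- A group comparison by SnPM of a within-subject between-bin contrast on log source power, permuting group labels over subjects. The log scale turns a proportional offset into an additive one, which cancels.
- For falling asleep, either bins 8–9 minus bins 2–3, following Figure 3, or a group-by-bin test over all ten bins after removing each subject's own mean over bins. For spontaneous arousals, the group-by-bin form is safer because it needs no anchor at arousal onset.
- A statement of how bins enter the level maps (singly or averaged) and of the correction over bins.
- A rule of interpretation: statements about altered progression rest on the between-bin contrast. Level maps are reported alongside it for the raised high-frequency sources in Hypothesis 2.

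Fixing the contrast in advance is preferable to subtracting the first bin, which would erase an abnormality already present there.

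The cost is a few lines of text and a little more analysis, on the same recordings and software. The downside is a noisier contrast if bins correlate weakly within a person; averaging two bins at each end limits this.

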4.5 Data and Record Keeping

Self-report data will be collected using electronic (e.g., computer tasks or questionnaires) and paper-based (e.g., paper questionnaires and interviews) formats. The study data will be managed by trained research personnel, including the investigators, a study coordinator, and approved research assistants. Coded data will be retained for at least 5 years or until the study is completed, whichever is longer. At that time, the research information will either be destroyed or all the information that identifies subjects will be removed from the study results and the key code will be destroyed.

4.5.1 Confidentiality Protections

All participants are assured of confidentiality of the information obtained during their participation. All participants are assigned a subject number for the internal purposes of the research, and the patients' identity is indicated only by their subject number and initials. Data (including audio and video recordings of mental health assessments and sleep studies) will be stored in a secure (password-protected and firewalled) database that is only accessible by study personnel. Subjects will be recognizable (i.e., face and voice) in the recordings. Paper copies of questionnaires or other data will be stored in locked cabinets in locked offices at UW-Psychiatry or Wisconsin Sleep. There will be a paper and electronic copy of the key code linking participants' names to the data through a participant identification number. The paper copy of the key code will be kept in a locked filing cabinet that is only accessible by study personnel with permitted access to PHI, and the electronic copy of the key code is stored in a secure (password-protected and firewalled) database separate from the main database that is only accessible by study personnel with permitted access to PHI. The full electronic database will contain the participant's unique study identifier and some date elements (such as visit date), but will otherwise be clean of identifiers. Participants will be advised that confidentiality could be breached in the event of an audit by the parent institution or the sponsor. All audio and video recordings of mental health assessments and sleep studies will be destroyed (i.e., erased from the electronic database) at the end of the study (i.e., once recruitment is complete and all necessary information, such as validity of assessments, is taken from the recordings).

Collection of sensitive information about participants will be limited to the amount necessary to achieve the aims of the current study. Screening interviews and other study contact that could potentially reveal private or harmful information will always be conducted in private

Insomnia and Sleep Patterns Study

